1.2 Purpose

[figure not shown]
Study CCFZ533B2201 (TWINSS) is a double-blinded Phase IIb study enrolling two distinct populations of patients with SjS and is defined as the "core study". Study CCFZ533B2201E1

[figure not shown]
is designed as a 1-year extension to the core study. The extension study will be open only to eligible participants from the TWINSS core study who, in the opinion of the Investigator, may potentially derive clinical benefit from continued administration of CFZ533 (iscalimab). The primary purpose of this 1-year extension study is to provide additional safety and tolerability information of the two doses of iscalimab (iscalimab 600 mg and 300 mg) administered via prefilled syringes (PFS). Additionally, this extension study will further explore the pharmacokinetics (PK) and efficacy of iscalimab 600 mg and 300 mg doses. Key additional safety data will be used to better understand the overall safety profile of iscalimab at two dose levels and potentially inform study design elements of subsequent clinical studies (i.e. Phase III).

2 Objectives and endpoints

Table 2-1 Objectives and related endpoints

Objective(s)	Endpoint(s)
Primary objective(s)	Endpoint(s) for primary objective(s)

To evaluate the safety and tolerability of iscalimab at two dose levels (600 mg and 300 mg) in patients with SjS, who participated in the TWINSS core study, CCFZ533B2201	
Incidence of Treatment-emergent adverse events (TEAEs)/ serious adverse events (SAEs) Routine hematology and clinical chemistry laboratory test results at analysis visits up to end of study Vital signs at analysis visits up to end of study
Secondary objective(s)	Endpoint(s) for secondary objective(s)

To assess the pharmacokinetics (PK trough levels) and dose-exposure relationship of iscalimabTo assess immunogenicity of iscalimab	
Free iscalimab concentration in plasma during the treatment (C_{trough}) and follow-up (up to end of study) periodsIncidence of anti-iscalimab antibodies in plasma at analysis visits up to end of study

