6.2.2 Prohibited medication

Use of treatments displayed in the below table is not allowed in study periods as indicated.

Table 6-2 Prohibited medication

Medication	Prohibited in Study Period	Action to be taken
Other experimental therapies	All	Study treatment discontinuation required, participants should remain in the study and follow visit schedule
Other biologics (for treatment of autoimmune diseases e.g., SjS, SLE, RA)	All	Study treatment discontinuation required, participants should remain in study and follow visit schedule

Medication	Prohibited in Study Period	Action to be taken
DMARDs or other immune suppressive agents or changes in an existing DMARD regimen (hydroxychloroquine, methotrexate, azathioprine)	Treatment period	Study treatment discontinuation may be required on a case-by-case basis
Prednisone >10 mg (or equivalent other corticosteroid)	Treatment period	Study treatment discontinuation may be required on a case-by-case basis
Intravenous or oral cyclophosphamide; oral cyclosporine; oral MMF	All	Study treatment discontinuation required, participants should remain in the study and follow visit schedule
Existing co-medications observed to cause in an individual patient a major side effect of dry mouth/eyes. Examples include antihistamines, antidepressants, anticholinergics, sedatives, antipsychotic drugs, anti-Parkinson agents A comprehensive guide to medications with documented effects on salivary gland function or symptoms has been published by Wolff et al 2017 (please see the footnote).	Treatment period	Study treatment discontinuation may be required on a case-by-case basis
Live/attenuated vaccine	During treatment and for at least 14 weeks thereafter	Study treatment discontinuation required, participants should remain in the study and follow visit schedule

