2.1.1.3 Baseline and post-baseline definitions

Baseline (Week 60E1) is defined as the last assessment (including unscheduled visits) obtained before the first dose of study treatment in extension study. All assessments obtained after first dose of study treatment at extension study are considered as post-baseline unless otherwise specified.

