2.4 Safety analyses

All safety endpoints (i.e., adverse events, laboratory data, and vital signs in extension study will be summarized by treatment for all subjects of the safety set.

Adverse events (AEs)

All adverse events in extension study are summarized based on treatment emergent only. The definition for "treatment emergent" is as below:

TEAE includes all events up to the last dose date plus 14 weeks (98 days) or the end of the entire study period (including the safety follow-up period), whichever occurred earlier. A listing of all adverse events during the study will be produced, with those defined as TEAE for the study treatment period with "treatment emergent" flag displayed.

The number and percentage of patients with treatment emergent adverse event (TEAE) will be summarized for the following:

- by treatment, primary system organ class and preferred term
- by treatment, primary system organ class, preferred term and maximum severity
- by treatment, Standardized MedDRA Query (SMQ) and preferred term.

Summaries will also be provided for study treatment related adverse events, serious adverse events, treatment related serious adverse events, deaths, and adverse events leading to permanent discontinuation of study-drug.

If a particular AE 'severity' is missing, this variable will be listed as missing and treated as missing in summaries. If a subject reported more than one adverse event with the same preferred term, the adverse event with the greatest severity will be presented. If a subject reported more than one adverse event within the same primary system organ class, the subject will be counted only once with the greatest severity at the system organ class level, where applicable.

The most common adverse events reported ($\geq 5\%$ in any group for each preferred term in the table by PT or $\geq 5\%$ in any group for each SMQ table) will be presented in descending frequency according to its incidence in all subjects starting from the most common event.

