2.4.3 Laboratory data

Only data from the central labs will be used for analysis in this section unless otherwise specified.

The summary of laboratory evaluations in extension study will be presented for two groups of laboratory tests (hematology and serum chemistry).

Descriptive summary statistics for the change from baseline to each study visit in extension study will be presented by laboratory test and treatment group. Change

Novartis	For business use only	Page 20
SAP Amendment 3		CCFZ533B2201E1

from baseline will only be summarized for subjects with both baseline and post baseline values and will be calculated as:

change from baseline = post baseline value – extension baseline value

For laboratory test values below Lower Level of Quantification (LLQ) or above Upper Level of Quantification (ULQ) will be imputed as LLQ or ULQ value, respectively. These laboratory values will be displayed in listings using the standard unit with the reported sign ("<" or ">")."

The following laboratory parameters will be analyzed with respect to numerical Common Terminology Criteria for Adverse Events (CTCAE) grades, given in Table 2-3: hemoglobin, platelets, white blood cell count, neutrophils, lymphocytes, creatinine, total bilirubin (TBL), alanine aminotransferase (ALT), aspartate aminotransferase (AST), alkaline phosphatase (ALP), and others.

The number and percentage of patients with clinically notable laboratory results after baseline (Week 60E1) will also be presented by laboratory test groups and parameters listed in section 4.2. These summaries will be split into hematology and chemistry. Central and local lab results will be displayed in separate tables for clinically notable laboratory results

CTCAE v5.00 Term	Grade 1	Grade 2	Grade 3	Grade 4
HGB decreased (Anemia)	<lln 100="" a="" l<="" td="" –=""><100 – 80 a/L	<80 g/L	Life-threatening consequences; urgent intervention indicated	</lln>	<100 – 80 a/L	<80 g/L	Life-threatening consequences; urgent intervention indicated
Platelet count	<lln 75.0<="" td="" –=""><75.0 - 50.0	<50.0 - 25.0		</lln>	<75.0 - 50.0	<50.0 - 25.0	
decreased	x10e9 /L	x10e9 /L	x10e9 /L	<25.0 x 10e9 /L
White blood cell decreased	<lln -="" 3.0="" x
10e9 /L</lln>	<3.0 - 2.0 x 10e9 /L	<2.0 - 1.0 x 10e9 /L	<1.0 x 10e9 /L
Neutrophil count decreased	<lln -="" 1.5="" x
10e9 /L</lln>	<1.5 - 1.0 x 10e9 /L	<1.0 - 0.5 x 10e9 /L	<0.5 x 10e9 /L

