Lymphocyte count decreased	<lln -="" 0.8="" x
10e9/L</lln>	<0.8 - 0.5 x 10e9 /L	<0.5 - 0.2 x 10e9 /L	<0.2 x 10e9 /L
Creatinine increased	>ULN - 1.5 x ULN	>1.5 - 3.0 x ULN	>3.0 - 6.0 x ULN	>6.0 x ULN
TBL increased	>ULN - 1.5 x ULN	>1.5 - 3.0 x ULN	>3.0 - 10.0 x ULN	>10.0 x ULN
ALT increased	>ULN - 3.0 x ULN	>3.0 - 5.0 x ULN	>5.0 - 20.0 x ULN	>20.0 x ULN
AST increased	>ULN - 3.0 x ULN	>3.0 - 5.0 x ULN	>5.0 - 20.0 x ULN	>20.0 x ULN
ALP increased	>ULN - 2.5 x ULN	>2.5 - 5.0 x ULN	>5.0 - 20.0 x ULN	>20.0 x ULN
GGT increased	>ULN - 2.5 x ULN	>2.5 - 5.0 x ULN	>5.0 - 20.0 x ULN	>20.0 x ULN
INR increased	>1.2 - 1.5 x	>1.5 - 2.5	>2.5	-

Table 2-3 CTCAE grades for laboratory parameters to be analyzed

Shift tables will be presented comparing baseline laboratory result (CTCAE grade) with the worst results (expressed in CTCAE grade) during the treatment phase analyzed.

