2.4.4.2 Vital signs

Analysis in vital sign measurement using descriptive summary statistics for the change from baseline for each post-baseline visit will be performed by vital sign and treatment group. Change from baseline will only be summarized for subjects with both baseline and post-baseline values and will be calculated as:

change from baseline = post-baseline value – extension baseline value

The number and percentage of subjects with newly occurring notable vital signs will be presented. Criteria for notable vital sign abnormalities are provided in Table 2-5 below. A listing of subjects with newly occurring notably abnormal vital signs will be provided.

Table 2-5	Criteria for notable vital sign abnormalities
-----------	---

Vital sign (unit)	Notable abnormalities
Systolic blood pressure (mmHg)	Either an increase of \ge 30 that results in \ge 180 or $>$ 200 (mm/Hg) OR a decrease of \ge 30 that results in \le 90 or $<$ 75 (mm/Hg)
Diastolic blood pressure (mmHg)	Either an increase of ≥ 20 that results in ≥ 105 or > 115(mm/Hg) OR a decrease of ≥20 that results in ≤ 50 or < 40 (mm/Hg)
Pulse (bpm)	> 100 bpm or <40 bpm

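### Notable laboratory and vital-sign counts have no limit from last dose, while TEAEs under the same primary objective stop at last dose + 98 days

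*SAP*

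**What the plan says.** Adverse events, laboratory results and vital signs are all endpoints of the one primary objective (Protocol Table 2-1 and 12.4.1).

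- **Adverse events.** SAP 2.4: "TEAE includes all events up to the last dose date plus 14 weeks (98 days) or the end of the entire study period", whichever comes first. SAP section 3 records this as a change from the protocol definition. It records no matching change for laboratory or vital-sign data.
- **Laboratory, by visit.** SAP 2.4.3: "Descriptive summary statistics for the change from baseline to each study visit in extension study will be presented by laboratory test and treatment group".
- **Laboratory, notable values.** SAP 2.4.3: "The number and percentage of patients with clinically notable laboratory results after baseline (Week 60E1) will also be presented". No end point is given.
- **Laboratory, shift tables.** SAP 2.4.3 compares baseline with the "worst results (expressed in CTCAE grade) during the treatment phase analyzed". The SAP does not define that phase.
- **Vital signs.** SAP 2.4.4.2: "Analysis in vital sign measurement using descriptive summary statistics for the change from baseline for each post-baseline visit will be performed". Newly occurring notable values are also counted, with no end point.
- **Post-baseline.** SAP 2.1.1.3: "All assessments obtained after first dose of study treatment at extension study are considered as post-baseline unless otherwise specified".

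Safety Set summaries are shown under the 600 mg and 300 mg groups.

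The documents describe visits after stopping in two ways. For other biologics, experimental therapies, cyclophosphamide, cyclosporine, MMF and live vaccines, Protocol Table 6-2 gives, in nearly identical words for each, this action: "Study treatment discontinuation required, participants should remain in the study and follow visit schedule". Protocol 6.2 instead sends participants who need escape treatment into the safety follow-up period. Table 8-1 footnote 19 does the same for premature discontinuation, after the discontinuation (TD) visit.

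**The concern.** Two attribution rules serve one objective. Take a participant whose last dose is Day 169 and who attends Week 108 on Day 337, which is 168 days off drug. An infection starting that day is listed but is not a TEAE. A grade 3 neutrophil count from the same visit enters the notable count of the 300 or 600 mg group.

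The 98-day limit has a stated basis. Protocol 4.2 expects concentrations at about 14 weeks after the last 600 mg dose to be too low for pharmacodynamic activity in target tissues. On that reasoning, later values describe a participant who is no longer exposed. Under Table 6-2 that participant may be taking another drug that itself changes blood counts or chemistry. Notable categories tend to be sparse, so a few such values could alter how a dose group looks. No table shows the reader how many of the notable values arose this late.

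**Working it through.** **Inputs.** Dosing and visit weeks come from Protocol 6.7.2 and Table 8-1. Hematology and chemistry draws come from Table 16-5: every 4 weeks from Week 64 to Week 104, then Weeks 108, 112 and 120, which is 14 post-baseline draws. The TEAE limit of 98 days comes from SAP 2.4. Extension study day = 7 × (week − 60) + 1.

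**Step 1, the plan's own figure.** Week 106 (last planned dose) is Day 7 × 46 + 1 = 323. Week 120 is Day 7 × 60 + 1 = 421. The difference is 421 − 323 = 98 days, exactly the TEAE limit. For a participant who completes dosing, TEAE coverage and laboratory coverage coincide at nominal days.

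**Step 2, early stoppers who follow the visit schedule to Week 120 (Table 6-2).** The draws fall on Days 29, 57, 85, 113, 141, 169, 197, 225, 253, 281, 309, 337, 365 and 421. TEAE limit = last-dose day + 98; count the draws after it.

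| Last dose | TEAE limit | Days off drug at Week 120 | Draws after the limit |
|---|---|---|---|
| Week 64, Day 29 | Day 127 | 392 | 10 of 14 |
| Week 72, Day 85 | Day 183 | 336 | 8 of 14 |
| Week 84, Day 169 | Day 267 | 252 | 5 of 14 |
| Week 96, Day 253 | Day 351 | 168 | 2 of 14 |
| Week 104, Day 309 | Day 407 | 112 | 1 of 14 |
| Week 106, Day 323 | Day 421 | 98 | 0 of 14 |

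The vital-sign windows in SAP Table 2-1 match the laboratory windows from Week 68 on, so the late visits are the same.

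**Step 3, early stoppers who go into follow-up (Protocol 6.2, footnote 19).** Assume the TD visit is 14 days after the last dose, mirroring Week 106 to Week 108. Twelve weeks of follow-up then give 14 + 84 = 98 days. If both 5-day visit windows run late, the figure is 98 + 10 = 108 days. The gap is between zero and about 10 days.

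**Step 4, where late values land.** SAP Table 2-1 ends the Week 108 window at EoP3 and starts Week 112 at EoP3 + 1. EoP3 is expanded only as the end of study period 3 and is not tied to last dose. If EoP3 were the TD visit, a last dose on Day 169 would put it at about Day 183. The Week 112 window would then run from Day 184 to Day 393, across the Week 88 to Week 108 windows. If EoP3 stays near Day 337, the same values go into the ordinary treatment-period rows. The SAP does not say which applies.

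**Step 5, number affected.** The documents give none. As an assumption only, 2% to 10% of the 206 enrolled is 206 × 0.02 = 4.1 to 206 × 0.10 = 20.6, or about 4 to 21 participants.

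**The case against.** The strongest reply is that the breadth is intended. The endpoint is "Routine hematology and clinical chemistry laboratory test results at analysis visits up to end of study", and Protocol 12.4.3 includes all data whatever intercurrent events occur. Starting a prohibited drug after stopping iscalimab is such an event. The tables are descriptive, and a row under a dose group is not a statement of cause. A clinically significant laboratory abnormality is also an AE under Protocol 10.1.1, so as an AE it does fall under the 98-day rule.

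This stands as far as it goes. A reader might infer that the SAP silently leaves off-drug data in its tables; the documents do not support that, because inclusion is declared. What 12.4.3 does not explain is why AEs have a limit from last dose and the other two components have none, or why no notable count is offered on the TEAE window.

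Three other objections also stand. First, not every laboratory table is open-ended, since the shift tables are restricted, though to an undefined phase. Second, some late values may already fall in follow-up rows through EoP3. Third, Protocol 9.1.1 asks only for AEs and treatments as a minimum after discontinuation, so fewer late draws may exist than the schedule implies.

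**Conclusion.** The mismatch is real and specific. TEAEs are limited to last dose + 98 days; notable laboratory counts, notable vital-sign counts and the by-visit summaries are not. Completers are untouched at nominal days. The gap concerns early stoppers who remain on the schedule under Table 6-2, at up to 10 of 14 draws for a last dose on Day 29 and 5 of 14 for Day 169. Under Protocol 6.2 and footnote 19 it is close to nil, given the assumed 14 days to the TD visit.

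Two stronger readings are tempting. One is that late values would dominate the rare notable categories. The documents give neither the number of participants who switch drugs nor any notable-category rate, so this cannot be supported. The other is that a 98-day cut would free the tables of other drugs' effects. It would not: with a last dose on Day 29, the draws on Days 57, 85 and 113 stay in the count even if another drug has been started, and TEAEs in that interval count as well.

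This is an inexpensive improvement in consistency. It does not show the primary safety analysis to be invalid.

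**What to change.** 1. In SAP 2.4.3 and 2.4.4.2, present notable counts for values up to the earlier of last dose + 98 days and end of study. Put later values in a separate off-treatment row or listing.
2. Keep the all-data by-visit tables that Protocol 12.4.3 calls for, and footnote at each visit the number of participants more than 98 days past their last dose.
3. Define the treatment phase used for the shift tables, and define EoP3 for participants who stop early, so that each value maps to one window.
4. Reconcile Protocol Table 6-2 with Protocol 6.2 and Table 8-1 footnote 19 on which visits follow discontinuation. The size of the gap cannot be settled until this is done.

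The cost is one date condition in the laboratory and vital-sign programs and a few definitions. A few late values move out of the main notable count, but none is discarded. The change aligns attribution with the TEAE window and does not separate out drugs started within 98 days of the last dose.

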12.4.2 Statistical model, hypothesis, and method of analysis

Only descriptive statistics will be provided, no inferential statistics will be conducted.

Adverse events:

Treatment emergent adverse events (TEAEs) will be summarized. Only primary paths within MedDRA will be considered for AE reporting. The definition for “treatment emergent” is as follows:

- Events started on or after the first dose of study treatment or events present prior to the first dose of study treatment but increased in severity based on preferred term;
- AEs observed four weeks after last study-drug administration will not be considered as treatment-emergent

AEs will be summarized by presenting, for each treatment group, the number and percentage of participants having any AE, having an AE in each primary system organ class and having each individual AE (preferred term). Summaries will also be presented for AEs by severity and for study treatment related AEs. If a participant reported more than one AE with the same preferred term, the AE with the greatest severity will be presented. If a participant reported more than one AE within the same primary system organ class, the participant will be counted only once with the greatest severity at the system organ class level, where applicable.

SAEs will also be summarized.

Separate summaries will be provided for deaths, SAEs, and other significant AEs leading to discontinuation.

All AEs including non-treatment emergent AEs will be listed.

Laboratory data:

The summary of laboratory evaluations will be presented for two groups of laboratory tests (hematology and serum chemistry). Descriptive summary statistics for the change from baseline to each study visit will be presented. These descriptive summaries will be presented by laboratory test and treatment group. Change from baseline will only be summarized for participants with both baseline and post-baseline values. For each parameter, the maximum change from baseline will be analyzed analogously. Number and percentage of participants with notable abnormalities will be summarized.

Vital signs:

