2.4.4 Other safety data

2.4.4.1 ECG

A listing of all newly occurring or worsening abnormalities (based on the treatment period/study period) will be provided, as well as a by-subject listing of all quantitative ECG parameters. Notable abnormal QTc will be defined as:

QTc > 500 msec

QTc > 480 msec

QTc > 450 msec

QTc changes from baseline > 30 msec

QTc changes from baseline > 60 msec

PR > 250 msec

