4.2 AEs coding/grading

Adverse events will be coded according to MedDRA version 22.0 or later

Laboratory parameters derivations

Clinically notable laboratory values

Biochemistry

- 1. ALT (SGPT): ≥3xULN
- 2. AST (SGOT): \geq 3xULN
- 3. Elevation of AST and/ or ALT (>3xULN) accompanied by elevated bilirubin (>1.5xULN, >2xULN)
- 4. Any elevations of bilirubin; elevated total bilirubin (TBL) to >2x ULN
- 5. Gamma-Glutamyltransferase (GGT): >3x ULN
- 6. Creatinine (serum): ≥3x ULN
- 7. Creatinine clearance (CrCl) (Cockroft-Gault formula): ≥25% decrease from baseline
- 8.

Hematology

- 1. Hemoglobin: ≥ 20 g/L decrease from baseline or < 100 g/L
- 2. Platelet count (per CTCAE v5.0)
 - a. CTC Grade 1: <Lower Limit of Normal (LLN) 75 x 10⁹/L
 - b. CTC Grade 2: $<75 50 \times 10^{9}/L$
 - c. CTC Grade 3: $<50 25 \times 10^{9}/L$
 - d. CTC Grade 4: <25x 10⁹/L
- ^{3.} White blood cell count (per CTCAE v5.0)
 - a. CTC Grade 1: <LLN 3 x 10⁹/L
 - b. CTC Grade 2: $<3 2 \times 10^9/L$
 - c. CTC Grade $3: <2 1 \ge 10^9/L$
 - d. CTC Grade 4: $<1 \times 10^{9}/L$
- 4. Absolute neutrophils (per CTCAE v5.0)
 - a. CTC Grade 1: <LLN 1.5 x 10⁹/L
 - b. CTC Grade 2: $<1.5 1 \times 10^{9}/L$
 - c. CTC Grade 3: $<1 0.5 \times 10^{9}/L$
 - d. CTC Grade 4: $<0.5 \times 10E^{9}/L$
- 5. Absolute lymphocytes: <LLN
- 6. Absolute eosinophils: $\geq 2.5x$, $\geq 3x$ ULN

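### The notable-laboratory count in SAP 2.4.3 sets no condition on the Week 60E1 value, so for absolute cut-offs it mixes abnormalities carried over from baseline with new ones

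*SAP*

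**What the plan says.** For laboratory tests, SAP 2.4.3 plans that the "number and percentage of patients with clinically notable laboratory results after baseline (Week 60E1) will also be presented", using the criteria in SAP 4.2. Nothing there refers to whether the criterion was already met at Week 60E1, and no denominator is given. SAP Table 2-2 takes the most extreme value in each window for notable abnormalities, again without reference to baseline.

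The neighbouring safety analyses do make the distinction. For vital signs: "The number and percentage of subjects with newly occurring notable vital signs will be presented" (SAP 2.4.4.2). For ECG: "A listing of all newly occurring or worsening abnormalities (based on the treatment period/study period) will be provided" (SAP 2.4.4.1).

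Most SAP 4.2 criteria are absolute limits, for example "Absolute lymphocytes: <LLN", and platelets, white cells and neutrophils from CTCAE Grade 1 upward. Creatinine clearance is judged wholly by change from baseline. Hemoglobin is mixed: "Hemoglobin: ≥ 20 g/L decrease from baseline or < 100 g/L".

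SAP 2.4.3 also plans two outputs that use baseline. One is by visit: "Descriptive summary statistics for the change from baseline to each study visit in extension study will be presented by laboratory test and treatment group". The other is by grade: "Shift tables will be presented comparing baseline laboratory result (CTCAE grade) with the worst results (expressed in CTCAE grade) during the treatment phase analyzed".

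Protocol 12.4.2 states for laboratory data: "Number and percentage of participants with notable abnormalities will be summarized". Its sentence for vital signs is nearly identical and equally unrestricted.

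**The concern.** A notable-value table in a safety report is normally read as what happened on treatment. Here, a participant below LLN for lymphocytes at Week 60E1 who stays there is counted in the same cell as one who fell below LLN after starting the extension. A reader of that table cannot tell them apart.

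This matters because laboratory results belong to the primary safety objective, and because the two dose groups are not randomised. Under Protocol 6.1.3, the extension dose depends on the core-study dose and on response, so nothing makes the groups alike in baseline blood counts. Stable azathioprine and methotrexate are allowed (Protocol 6.2.1), and there is no placebo arm (Protocol 4.3). If more participants in one dose group start below a limit, the side-by-side percentages differ for that reason alone.

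**Working it through.** **1. Counting rules side by side**

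| Data | Where | Condition on baseline |
|---|---|---|
| Laboratory, notable | SAP 2.4.3 and 4.2 | none |
| Vital signs, notable | SAP 2.4.4.2 | newly occurring |
| ECG listing | SAP 2.4.4.1 | newly occurring or worsening |
| Laboratory and vital signs, notable | Protocol 12.4.2 | none for either |

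The SAP therefore narrowed vital signs and left laboratory tests as the protocol had them.

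**2. Which criteria are affected (SAP 4.2)**

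- Can already be met at baseline: lymphocytes below LLN; platelets, white cells and neutrophils from Grade 1; hemoglobin below 100 g/L; ALT and AST; total bilirubin above 2 × ULN; GGT above 3 × ULN; AST/ALT combined with bilirubin; creatinine; eosinophils.
- Cannot be met at baseline: creatinine clearance fall of at least 25%; hemoglobin fall of at least 20 g/L.

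**3. What the shift tables recover (SAP Table 2-3)**

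- Recovered: lymphocytes below LLN (Grade 1 or worse), the platelet, white cell and neutrophil grades, and hemoglobin below 100 g/L (the Grade 1/2 boundary).
- Not recovered: eosinophils and the AST/ALT-plus-bilirubin combination, which are not in the table. Bilirubin above 2 × ULN lies inside Grade 2 (>1.5 to 3.0 × ULN), and GGT above 3 × ULN inside Grade 2 (>2.5 to 5.0 × ULN).
- Also not recovered: follow-up draws, because the shift tables cover the treatment phase. Protocol Table 16-5 has 12 draws from Week 64 to Week 108 (every 4 weeks), plus Weeks 112 and 120, so 2 of 14 fall outside.

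**4. Size**

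The plan states no laboratory rate, so there is no figure to reproduce. Let b be the share meeting the criterion at baseline, s the share of those who meet it at least once afterwards, and i the new-onset rate among the rest. All three are assumptions.

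- Count as worded: b·s + (1 − b)·i
- New cases over all participants: (1 − b)·i
- Excess: b·s

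With N = 206 (SAP 1.1), s = 80% and i = 5%:

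| b | As worded | New only | Excess |
|---|---|---|---|
| 0% | 5.0% (10.3) | 5.0% (10.3) | 0 |
| 5% | 8.75% (18.0) | 4.75% (9.8) | 4 points |
| 10% | 12.5% (25.8) | 4.5% (9.3) | 8 points |
| 20% | 20.0% (41.2) | 4.0% (8.2) | 16 points |

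Numbers in brackets are expected participants. For b from 0 to 30% and s from 50% to 100%, the excess runs from 0 to 30 points.

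For two groups with i = 10% and s = 1 in both, and b = 15% against 30%: 0.15 + 0.85 × 0.10 = 23.5% and 0.30 + 0.70 × 0.10 = 37.0%. That is a 13.5-point difference with no drug effect.

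**5. What the change would and would not remove**

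The last example assumes that i is the same in both groups. A simulation relaxes this: no drug effect, 14 post-baseline draws, LLN at −1.96 SD, one group's mean 1 SD lower, within-person correlation 0.60 or 0.75. In the lower group about 17% are below LLN at baseline.

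| Correlation | As worded, lower vs other group | New only, at-risk denominator |
|---|---|---|
| 0.60 | 55% vs 15% (gap 40 points) | 47% vs 13% (gap 34) |
| 0.75 | 45% vs 11% (gap 34 points) | 35% vs 9% (gap 26) |

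Of those counted in the lower group, 29% (correlation 0.60) and 36% (0.75) were already low at baseline. Removing them leaves 34/40 = 85% and 26/34 = 76% of the spurious gap, because participants just above LLN cross it by ordinary within-person variation.

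**The case against.** The strongest reply is that the count is one output among several. It is presented in addition to change from baseline by visit and the shift tables, and the shift tables already separate baseline from on-treatment grade for the commonest examples: lymphocytes, neutrophils, white cells, platelets and hemoglobin. An inclusive count of any post-baseline notable value is a legitimate safety display, and the study is descriptive throughout. This stands and limits the weight of the point. It does not cover the criteria and draws in step 3 that the shift tables miss, and it does not make the count itself readable.

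A reader might go further and infer that the primary laboratory table reports prevalence instead of treatment-emergent incidence. The documents do not support that. The primary laboratory endpoint is test results at visits up to the end of study (Protocol Table 2-1, SAP Table 1-1), and it is nowhere defined as treatment-emergent. The count is not prevalence either: it mixes persistent and new cases, and its change-based criteria are new by definition.

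Nor does the SAP expressly direct that pre-existing abnormalities be counted. That is the literal effect of a rule with no baseline condition. If the sponsor meant new cases only, the text does not say so, and two programmers could produce different tables. The laboratory wording is also not a departure from the protocol, which has no such restriction.

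**Conclusion.** The point holds in limited form. For the absolute-limit criteria in SAP 4.2, the notable-laboratory count as worded mixes carried-over and new abnormalities, which the SAP avoids for vital signs and ECG. The shift tables make up for this for most parameters, but not for eosinophils, combined AST/ALT with bilirubin, the bilirubin 2 × and GGT 3 × ULN cut-points, or Weeks 112 and 120.

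The size cannot be determined from the documents, which give no baseline abnormality rates. The excess is b·s, from zero upward, and the figures above are illustrations on assumed rates.

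It would be tempting to conclude that restricting the table to new cases makes the dose comparison fair. It would not: in the no-effect simulation roughly three quarters or more of the gap remained. Assignment by prior dose and response leaves confounding that no counting rule removes, so dose differences in this table should not be read as causal in either form.

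**What to change.** In SAP 2.4.3, define notable laboratory results as newly occurring or worsened relative to Week 60E1: the criterion was not met at baseline, or, for graded parameters, the result is at least one CTCAE grade worse.

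State the denominators:
- Newly occurring: participants with a baseline and a post-baseline value who did not meet the criterion at baseline.
- Worsened grade: all participants with both values who could still worsen.

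Keep the all-values count and show beside it the number already notable at baseline, so that no safety information is lost. Add a sentence that differences between the dose groups in this table are descriptive and not causal, given the non-randomised assignment.

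The cost is a short SAP edit and one extra programming flag. Denominators become slightly smaller for criteria that are common at baseline. No additional data are needed.
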